#### **5.5.3.2.6 Inpatient Hospitalizations due to Epilepsy**

The number of inpatient epilepsy-related hospitalizations since the previous visit are recorded at every visit starting from Visit 2 (Day 1).

The number of patients with inpatient epilepsy-related hospitalizations will be presented for the baseline and treatment periods.

#### **5.5.3.2.7 Sleep Disruption 0-10 Numerical Rating Scale**

The sleep disruption 0-10 NRS will be performed at Visits 2 (Day 1), 3, 4, 6 and 8 (end of treatment). The patient's caregiver will be asked:

- "On a scale of '0 to 10', please indicate the number that best describes your child's sleep disruption in the last week."

The markers range from 0 = slept extremely well, to 10 = unable to sleep at all.

The sleep disruption 0-10 NRS score, recorded at each visit, will be summarized, on a continuous scale, by treatment group. The change from baseline (Visit 2) will also be included.

The change from baseline to the end of treatment visit and last visit (if different to the end of treatment) will be analyzed using ANCOVA. The model will include baseline and age group as covariates and treatment group as fixed factor. Analysis performed at the last visit will be considered the main analysis for this endpoint, with the analysis at the end of treatment visit considered a sensitivity analysis.

The estimated least squares means, treatment difference, together with the 95% CIs and p-value will be presented.

#### **5.5.3.2.8 Epworth Sleepiness Scale**

The ESS is a questionnaire that provides a measure of a person's general level of daytime sleepiness, or their average sleep propensity in daily life. The ESS contains 8 questions that are rated on a 4-point numerical scale (0–3). The total ESS score is the sum of the 8 item-scores and can range between 0 and 24. Higher total scores represent greater levels of daytime sleepiness.

The ESS questionnaire will be completed at Visits 2 (Day 1), 3, 4, 6 and 8 (end of treatment) by the patient's caregiver.

The total score, recorded at each visit, will be summarized, on a continuous scale, by treatment group. The change from baseline (Visit 2) will also be included.

The change from baseline in the total score to the end of treatment visit and last visit (if different to the end of treatment) will be analyzed using the same ANCOVA approach as specified in Section 5.5.3.2.7. Analysis performed at the last visit will be considered the main analysis for this endpoint, with the analysis at the end of treatment visit considered a sensitivity analysis.

Missing data arising from missing individual questions will be handled according to Section 5.1.1.2.1.

### 5.5.3.2.9 Quality of Life in Childhood Epilepsy

The QOLCE is a parent-reported questionnaire that evaluates health related quality of life in children aged 4–18 years old. It contains 76 items with 16 subscales covering 7 domains of life function: physical activities, social activities, cognition, emotional well-being, behavior, general health, and general quality of life. The QOLCE will be completed by the parent or caregiver at Visits 2 (Day 1) and 8 (end of treatment).

All items in the questionnaire are rated on a 5-point or 6-point categorical scale. Based on the responses to the items in each domain, scores for 16 subscales are derived. The subscales are presented in [Table 4](#).

**Table 4 QOLCE Subscales**

Subscale	Item Domains	Items Used
Physical Restrictions	Physical Activities	3.1 (a to j)
Energy/Fatigue	Physical Activities	3.2 (a,b)
Attention/Concentration	Cognition	5.1 (a,d,e,f,g)
Memory	Cognition	5.1 (j,k,l,m,n,o)
Language	Cognition	5.1 (p,q,r,s,t,u,v,w)
Other Cognitive	Cognition	5.1 (b,c,h)
Depression	Emotional Well-Being	4.1 (a,d,e,l)
Anxiety	Emotional Well-Being	4.1 (b,g,j,n,o,p)
Control/Helplessness	Emotional Well-Being	4.1 (c,f,h,i)
Self-esteem	Emotional Well-Being	4.1 (k,m,q,r,s)
Social Interactions	Social Activities	6.1 (c,f,h)
Social Activities	Social Activities	6.1 (a,e) and 6.2
Stigma Item	Social Activities	6.1 (i)
Behavior	Behavior	7.1 (a,c,f,g,h,i,j,k,l,m,o,q,r,s,t)
General Health Item	General Health	8.1
Quality of Life Item	Quality of Life	9.1

Items within each subscale will be coded and linearly transformed, according to the methods of Sabaz et al., to a score of 0 to 100, where 0 represents the lowest or poorest category and 100 represents the highest level of functioning.

A subscale score is calculated for each subscale by computing the mean of the items within the subscale. An ‘Overall Quality of Life Score’ can be calculated by taking the mean of the subscale scores.

Individual items will be listed only. The subscale scores and the overall quality of life score, recorded at each visit, will be summarized, on a continuous scale, by treatment group. The change from baseline (Visit 2) will also be included.

The change from baseline to the end of treatment visit, for the overall quality of life score, and the attention/concentration, memory, language, other cognitive, social interactions and behavior subscale scores only, will be analyzed using the same ANCOVA approach as specified in Section 5.5.3.2.7. Exploratory analyses may also be performed on other subscale scores.

Missing data will be handled according to Section 5.1.1.2.2.

### 5.5.3.2.10 Vineland Adaptive Behavior Scales, Second Edition

The Vineland-II is an individually administered instrument for assessing adaptive behaviors. The Vineland-II assessments will be made at Visits 2 (Day 1), 3, 4, 6 and 8 (end of treatment).

The Vineland-II consists of 44 adaptive behavior domains and a maladaptive behavior domain. The details of each domain are presented in [Table 5](#).

**Table 5 Content Description of the Vineland-II**

Domains and Subdomains	Number of Items	Age Range (Years)	Content
Adaptive Behavior Domains			
Communication Domain	99	$\geq 0$	
Receptive	20	$\geq 0$	How the individual listens and pays attention, and what he or she understands
Expressive	54	$\geq 0$	What the individual says, how he or she uses words and sentences to gather and provide information
Written	25	$\geq 3$	What the individual understands about how letters make words, and what he or she reads and writes
Daily Living Skills Domain	109	$\geq 0$	
Personal	41	$\geq 0$	How the individual eats, dresses and practices personal hygiene
Domestic	24	$\geq 1$	What household tasks the individual performs
Community	44	$\geq 1$	How the individual uses time, money, the telephone, the computer and job skills
Socialization Domain	99	$\geq 0$	
Interpersonal Relationships	38	$\geq 0$	How the individual interacts with others
Play and Leisure Time	31	$\geq 0$	How the individual plays and uses leisure time
Coping Skills	30	$\geq 1$	How the individual demonstrates responsibility and sensitivity to others
Motor Skills Domain	76	$\geq 0$ to $< 7$	
Gross	40	$\geq 0$ to $< 7$	How the individual uses arms and legs for movement and coordination
Fine	36	$\geq 0$ to $< 7$	How the individual uses hands and fingers to manipulate objects
Maladaptive Behavior Domain			
Maladaptive Behavior Index	36	$\geq 3$	A composite of Internalizing, Externalizing, and Other types of undesirable behavior that may interfere with the individual's adaptive functioning
Internalizing (Section A)	11	$\geq 3$	
Externalizing (Section B)	10	$\geq 3$	
Other (Section C)	15	$\geq 3$	
Maladaptive Behavior Critical Items	14	$\geq 3$	More severe maladaptive behaviors that may provide clinically important information

For each subdomain, a raw score is calculated based on the responses to the individual items within the subdomain. For the maladaptive behavior index, the raw score is the sum

of the 3 subdomain raw scores. Using the raw score and the patients' age the following are obtained:

- v-Scale Score: a type of standard score scale (standardized by age) to describe an individual's relative level of functioning. Ranging from a score of 1 to 24.
- 90% CI for the v-Scale Score: a range of scores that has a certain likelihood of including the individual's true score.
- Adaptive Level: a means to describe an individual's performance using terms that are nearly universal (Low, Moderately Low, Adequate, Moderately High, High).
  - For the maladaptive behavior index and maladaptive behavior subdomains the adaptive levels are: Average, Elevated or Clinically Significant.
- Age Equivalent: the age at which the raw score is average. Not applicable for the maladaptive behavior index and maladaptive behavior subdomains.

For each adaptive behavior domain, the sum of the v-scale scores of the subdomains is used along with the patients' age to obtain the following:

- Standard Score (standardized by age). Ranging from a score of 20 to 160.
- 90% CI for the domain standard score.
- Percentile Rank: the percentage of people whom the individual outperformed in his or her age group.
- Adaptive Level (Low, Moderately Low, Adequate, Moderately High, High).
- Stanine: whole number score ranging from 1 to 9 and representing a specific range of percentile ranks.

An adaptive behavior composite can then be obtained using the sum of the adaptive behavior domain standard scores (excluding the motor skills domain for patients  $\geq 7$  years of age). The same derived information as the adaptive behavior domain is obtained for the adaptive behavior composite.

For the maladaptive behavior index, all items within each section must be answered for a raw score to be calculated. If any of the items are missing then the maladaptive behavior index score will be missing.

For the adaptive behavior subdomains, the derivation of the raw score allows for up to 2 missing values or answers of "Don't Know" within the items used for scoring. If there are more than 2 missing values or answers of "Don't Know" then the raw score will not be calculated and the subdomain score, domain score and adaptive behavior composite score will be missing.

The adaptive levels corresponding to the v-scale scores and standard scores are presented in [Table 6](#).

**Table 6 Adaptive Levels by v-Scale Scores and Standard Scores**

Adaptive Level	v-Scale Score for Subdomains and Maladaptive Behavior Index	Standard Score for Domains and Adaptive Behavior Composite
Adaptive Behavior Domains		
Low	1 to 9	20 to 70
Moderately Low	10 to 12	71 to 85
Adequate	13 to 17	86 to 114
Moderately High	18 to 20	115 to 129

High	21 to 24	130 to 160
Maladaptive Behavior Domain		
Clinically Significant	21 to 24	
Elevated	18 to 20	
Average	1 to 17	

The v-scale score from the 11 adaptive behavior subdomains, 3 maladaptive behavior subdomains and the maladaptive behavior index, and the standard score from the 4 adaptive behavior domains and the adaptive behavior composite, recorded at each visit, will be summarized, on a continuous scale, by treatment group. The change from baseline (Visit 2) will also be included.

The change from baseline to the end of treatment visit and last visit (if different to the end of treatment), for the 4 adaptive behavior domains, the adaptive behavior composite and the maladaptive behavior index only, will be analyzed using the same ANCOVA approach as specified in Section 5.5.3.2.7. Analysis performed at the last visit will be considered the main analysis for this endpoint, with the analysis at the end of treatment visit considered a sensitivity analysis.

The adaptive level from the 11 adaptive behavior subdomains, 4 adaptive behavior domains, the adaptive behavior composite, the 3 maladaptive behavior subdomains and the maladaptive behavior index, recorded at each visit, will be summarized, on a categorical scale, by treatment group.

The adaptive level from the 4 adaptive behavior domains, the adaptive behavior composite and the maladaptive behavior index only will be analyzed using ordinal logistic regression. Factors for treatment and age group will be included along with the baseline adaptive level as a covariate. The estimated odds ratios (GWP42003-P groups vs. placebo), 95% CI for the odds ratios, and the p-values testing the null hypothesis that the odds ratio is equal to 1, will be presented.

Each adaptive level for adaptive behavior will be coded with a score from 1 to 5, where 1 = Low, and 5 = High. Each adaptive level for the maladaptive behavior index will be coded with a score from 1 to 3, where 1 = Clinically Significant, and 3 = Average.

The individual responses within each domain will not be listed, only the derived information for each subdomain and domain will be listed.

#### 5.5.3.2.11 Cognitive Assessment Battery

The cognitive assessment battery will be administered at Visit 2 (baseline) and Visit 8 (end of treatment). The items are age specific and the age of the patient at entry is the age used when choosing the items to be given. Children and adults are to complete the battery as able. It is expected that a number of patients will only be able to complete part of the battery and some may not be able to complete it at all. Parents and/or caregivers are to complete certain items.

The battery items will only be administered to a sub-group of sites that have the expertise to conduct the test. Assessments are conducted by an experienced psychometrician.

A summary of the patient and parent measures are given in [Table 7](#).

**Table 7 Neuropsychological Protocol for Epilepsy Patients Treated with Cannabidiol – Patient and Parent Measures**

Category	Function	Measures	Age Range
Patient	Intelligence IQ	Wechsler Preschool and Primary Scale of Intelligence – Fourth Edition (WPPSI-4) Vocabulary, Matrix Reasoning	2;6 - 5;11 years
		Wechsler Abbreviated Scale of Intelligence – Second Edition (WASI-2) Vocabulary, Matrix Reasoning (Including Wechsler: ‘Digit Span’ subtest from Wechsler Intelligence Scale for Children – Fourth Edition (WISC-4) and Wechsler Adult Intelligence Scale - Fourth Edition (WAIS-4); ‘Coding’ subtest from WISC-4 & WAIS-4; ‘Bug Search’ from WPPSI-4)	6 - adult
	Attention/Executive Trail Making	Trail Making Test Delis–Kaplan Executive Function System (D-KEFS)	9 - adult
	Language Naming Fluency	Expressive One-Word Picture Vocabulary Test-4th Edition	2 - adult
		NEPSY-2 Word Generation	2 - 5 years
		F-A-S and Animals	6 - adult
	Visual-Spatial VMI	Developmental Test of Visual Motor Integration-6	2 - adult
Fine Motor Speed Pegs	Purdue Pegboard	4 - adult	
Parent	Executive	Behavior Rating Inventory of Executive Function (Parent and Teacher)	3 - 21 years
	Attention	Attention deficit hyperactivity disorder (ADHD) Checklist (Parent and Teacher)	All ages
	Mood/Anxiety	Behavior Assessment System for Children – Second Edition (BASC-2) (Parent and Teacher)	3 - 21 years
	Free-form report	Behavior Report Form (Parent and Teacher)	All ages

The following patient measures will be summarized, on a continuous scale, by treatment group at each visit and including the change from baseline using the score recorded on the CRF:

- Intelligence:
  - WPPSI-4 T score:
    - Receptive Vocabulary.
    - Matrix Reasoning.
    - Bug Search.
  - WASI-2 T score:
    - Vocabulary.
    - Matrix Reasoning.
  - WISC-4 and WAIS-4:
    - Coding scaled score.

- Digit Span (Forward, Backward, Longest forward, Longest Backward).
- Attention/Executive:
  - D-KEFS scaled scores.
- Language:
  - Expressive One-Word Picture Vocabulary Test-4th Edition scaled score.
  - NEPSY-2 Word Generation scaled score.
- Visual-Spatial:
  - Developmental Test of Visual Motor Integration-6 standard score.
- Fine Motor Speed:
  - Dominant hand, non-dominant hand and both hands Z scores.

The following parent measures will be summarized, on a continuous scale, by treatment group at each visit and including the change from baseline using the scored recorded on the CRF:

- Executive:
  - Behavior Rating Inventory of Executive Function T scores for indexes and composite.
- Mood/Anxiety:
  - BASC-2 T scores for composite scores.

The behavior report form will be summarized, on a categorical scale, by treatment at each visit.

The ADHD checklist consists of 18 questions, questions 1 to 9 relate to inattention and questions 10 to 18 relate to hyperactivity. A derived Inattention and Hyperactivity score can be calculated by taking the sum of the corresponding question responses, where 0 = 'Not at all' and 3 = 'Very much' and dividing by 9. A combined score can also be calculated by taking the sum of the responses from questions 1 to 18 and dividing by 18. The Inattention, Hyperactivity and combined scores will be summarized, on a continuous scale, at each visit and by treatment group. The change from baseline (Visit 2) will also be included.

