### **2.2 Secondary**

- To assess changes from baseline in convulsive and non-convulsive seizure frequency, duration, usage of rescue medication, number of inpatient hospitalizations due to epilepsy, sleep disruption, daytime sleepiness, quality of life, growth and development, and conduct behavioral and cognitive assessments in patients taking GWP42003-P as an adjunctive treatment, when compared with placebo.
- To determine the pharmacokinetics (PKs) of cannabidiol (CBD) and its major metabolites following single and multiple doses of GWP42003-P and to assess the presence of  $\Delta^9$ -tetrahydrocannabinol (THC) and its major metabolites in plasma and the presence of THC, CBD and their major metabolites in urine after multiple doses of GWP42003-P.
- To determine effects of GWP42003-P on plasma concentrations of concomitant antiepileptic drugs (AEDs), where available.
- To assess the safety of both GWP42003-P doses when compared with placebo.

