For number of hospitalizations due to epilepsy, sleep disruption, daytime sleepiness, QOLCE, cognitive function and behavior assessments, the data will be summarized at baseline, over the treatment period, and at each time point (or 28-day period, as appropriate) during the maintenance period. Changes from baseline to the average over the treatment period (or at the end of study) will be analyzed using ANCOVA (or appropriate non-parametric methods if data are found to be not normally distributed). The model will include baseline (where applicable) and age group as covariates and treatment group as a fixed factor. The estimated least squares means, treatment difference, together with the 95% CIs and p-value will be presented.

For changes in non-convulsive and total seizure frequency and changes in frequency of other seizure types the data will be summarized at baseline, over the treatment period, and at each time point (or 28-day period, as appropriate) during the maintenance period. Changes over the treatment period compared to baseline will be analyzed using the same analysis as the primary endpoint.

CGIC and CGICSD assessments recorded at the end of treatment will be analyzed with ordinal logistic regression using the proportional odds model.

Changes from baseline for IGF-1 levels will be summarized by treatment group and plotted against the Tanner Stages, weight, and height.

Tanner Stages will be evaluated and summarized descriptively at each time point in terms of frequency and proportions. Number (%) of patients with changes in Tanner Stages and the transition time between stages will be summarized by treatment group.

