#### **5.6.4.5 Growth and Development**

IGF-1 levels will be analyzed as part of the clinical laboratory testing. IGF-1 levels will be summarized on a continuous scale, including change from baseline, by treatment group.

Change from baseline to the end of treatment visit for IGF-1 levels will also be plotted against the Tanner Stages, weight, and height recorded at baseline.

The pubic hair growth (both sexes), genital (males only) and breast (females only) development of all adolescent patients (i.e., 10 to less than 18 years of age at the time of signing the informed consent form, or earlier if clinically indicated by onset of menarche or other signs of precocious puberty) will be assessed using Tanner Staging. The patients will undergo a discreet physical examination and be assigned a value under each category of Pubic Hair Growth (both sexes), Genitals (male patients only), and Breasts (female patients only).

Patients will be examined at Visit 2 (Day 1) and Visit 8 (end of treatment). Once a patient reaches a score of V (i.e., 5) the examination need not be performed again.

Tanner Stages will be summarized on a categorical scale, by treatment group.

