## 5.8 Changes in the Conduct of the Study or Planned Analysis

The identification of 3 key secondary endpoints and the hierarchical testing procedure were not defined in the protocol, but have been included in the SAP prior to unblinding.

Upon blinded review of IVRS data for the number of convulsive seizures greater than 30 minutes in duration and the number of non-convulsive seizures greater than 30 minutes in duration, it was determined that there were insufficient numbers of patients reporting these seizures to perform analyses planned in the protocol.

Upon blinded review of the number of patients with inpatient epilepsy-related hospitalizations, it was determined that there were insufficient numbers of patients to perform analyses planned in the protocol.

The protocol included changes from baseline in usage of rescue medication as an efficacy endpoint. However, due to inconsistencies in the collection of this data, no analyses are proposed.

The endpoint of number of patients experiencing a >25% worsening, -25 to +25% no change, 25–50% improvement, 50–75% improvement or >75% improvement in convulsive seizures from baseline has been updated to the following:

- Number of patients experiencing a >25% increase,  $\geq 0$  to  $\leq 25\%$  increase, >0 to <25% reduction,  $\geq 25$  to <50% reduction,  $\geq 50$  to <75% reduction or  $\geq 75\%$  reduction in convulsive seizures from baseline.

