Table 9.14.1.4	Analysis of the Vineland-II Adaptive Behavior Domain and Composite Adaptive Levels	ITT Analysis Set
Table 9.14.2.1	Summary of the Vineland-II Maladaptive Behavior Subdomain and Index Scores	ITT Analysis Set
Table 9.14.2.2	Summary of the Vineland-II Maladaptive Behavior Subdomain and Index Adaptive Levels	ITT Analysis Set
Table 9.14.2.3	Analysis of Change from Baseline in the Vineland-II Maladaptive Behavior Index Score	ITT Analysis Set
Table 9.14.2.4	Analysis of the Vineland-II Maladaptive Behavior Index Adaptive Level	ITT Analysis Set
Table 9.15.1	Summary of Cognitive Assessment Battery Patient Measures	ITT Analysis Set
Table 9.15.2.1	Summary of Cognitive Assessment Battery Parent Measures – Executive (Behavior Rating Inventory of Executive Function)	ITT Analysis Set
Table 9.15.2.2	Summary of Cognitive Assessment Battery Parent Measures – Attention (ADHD Checklist)	ITT Analysis Set
Table 9.15.2.3	Summary of Cognitive Assessment Battery Parent Measures – Mood/Anxiety (BASC-2)	ITT Analysis Set
Table 9.15.2.4	Summary of Cognitive Assessment Battery Parent Measures – Behavior Report Form	ITT Analysis Set
Table 9.16.1	Analysis of Time to Baseline Convulsive Seizure Frequency from the Start of the Treatment Period (Day 1)	ITT Analysis Set
Table 9.16.2	Analysis of Time to Baseline Convulsive Seizure Frequency from the Start of the Maintenance Period (Day 15)	ITT Analysis Set
Table 9.17.1	Analysis of Change from Baseline in Convulsive Seizure Free Days Per 28 Days During the Treatment Period	ITT Analysis Set
Table 9.17.2	Analysis of Change from Baseline in Convulsive Seizure Free Days Per 28 Days During the Maintenance Period	ITT Analysis Set
Table 9.18.1	Negative Binomial Regression Effect Modification Analysis of Convulsive Seizure Count during Baseline and Treatment Periods	ITT Analysis Set

Table Number	Title	Analysis Set
Table 9.18.2	Logistic Regression Effect Modification Analysis of Convulsive Seizure Responders ( $\geq 50\%$ Reduction) During the Treatment Period	ITT Analysis Set
Table 10.1	Summary of Exposure	Safety Analysis Set
Table 10.2	Summary of Expected Daily Volumes of IMP Taken Post-Titration	Safety Analysis Set
Table 11.1	Overall Summary of Treatment Emergent Adverse Events	Safety Analysis Set
Table 11.2	Summary of Treatment Emergent Adverse Events	Safety Analysis Set
Table 11.3	Summary of Treatment-Related Treatment Emergent Adverse Events	Safety Analysis Set

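### The SAP replaces the protocol's ANCOVA of the cognitive battery and its count of Tanner stage changes with plain summaries, and does not declare either change

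*SAP*

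**What the plan says.** The secondary objective (Protocol 2.2) covers "growth and development, and conduct behavioral and cognitive assessments in patients taking GWP42003-P as an adjunctive treatment, when compared with placebo".

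Protocol 13.6.3 sets the method. The relevant paragraph opens "For number of hospitalizations due to epilepsy, sleep disruption, daytime sleepiness, QOLCE, cognitive function and behavior assessments, the data will be summarized at baseline" and continues "Changes from baseline to the average over the treatment period (or at the end of study) will be analyzed using ANCOVA", with a non-parametric alternative if normality fails. The model has baseline and age group as covariates and treatment as a factor. The output is least squares means, the treatment difference, 95% CIs and a p-value. For puberty the same section says: "Number (%) of patients with changes in Tanner Stages and the transition time between stages will be summarized by treatment group".

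SAP 5.5.3.2.11 describes the battery output as "The following patient measures will be summarized, on a continuous scale, by treatment group at each visit and including the change from baseline", with matching text for the parent measures. SAP Appendix 5 (Table 13) agrees: Table 9.15.1 is titled "Summary of Cognitive Assessment Battery Patient Measures", and Tables 9.15.2.1 to 9.15.2.4 are also summaries. On Tanner staging, SAP 5.6.4.5 says: "Tanner Stages will be summarized on a categorical scale, by treatment group".

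SAP 5.8 explains that status epilepticus and hospitalization analyses were dropped (for hospitalizations, "it was determined that there were insufficient numbers of patients to perform analyses planned in the protocol") and that rescue medication will not be analyzed because collection was inconsistent. It mentions neither cognition nor Tanner staging. SAP 3.3.2.2 still places both endpoints under a heading that promises a comparison between groups.

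**The concern.** A comparison planned in the protocol has disappeared without a stated reason, and the SAP's endpoint section and methods section now disagree. Cognition is a named objective in children whose disease carries a poor cognitive prognosis. Group means with no adjusted difference and no CI show neither whether the battery scores differ from placebo nor how large an adverse effect the data exclude. For Tanner staging, frequencies at two visits give the marginal distribution in each arm but not how many patients moved.

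Disclosure matters separately. Protocol section 13 commits the study report to describing deviations from the final SAP. An analysis removed before the SAP is final is not such a deviation, so SAP 5.8 is where the reader should find it.

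**Working it through.** **Side-by-side reading.** The plan gives no figure specific to these endpoints. Its only power calculation concerns convulsive seizures and does not enter here.

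| Item | Protocol 13.6.3 | SAP | Declared in SAP 5.8? |
|---|---|---|---|
| Cognitive battery | ANCOVA, difference, 95% CI, p-value | By-group summary with change from baseline (5.5.3.2.11) | No |
| Tanner stage change | Number and percentage, descriptive | Not present; frequencies only (5.6.4.5) | No |
| Tanner transition time | Descriptive | Not present | No |
| Sleep, daytime sleepiness, QOLCE | ANCOVA | ANCOVA (5.5.3.2.7 to 5.5.3.2.9) | Not applicable |
| Behavior assessments (Vineland-II) | ANCOVA | ANCOVA (5.5.3.2.10) | Not applicable |
| Hospitalizations | ANCOVA | Number of patients (5.5.3.2.6) | Yes |

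Within one protocol paragraph, most endpoints keep their model, hospitalizations lose it with an explanation, and the battery loses it silently.

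**What a battery CI would look like.** The battery runs only at a sub-group of sites, and the documents give no expected number and no correlation. The ranges below are assumptions: n = 10 to 30 paired patients per arm, and baseline to end-of-treatment correlation r = 0.5 to 0.9. In SD units, by normal approximation, the 95% half-width is 1.96 × √[(2/n)(1 − r²)]. For n = 20 and r = 0.7 this is 1.96 × √(0.1 × 0.51) = 0.44.

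| n per arm | r = 0.5 | r = 0.7 | r = 0.9 |
|---|---|---|---|
| 10 | 0.76 | 0.63 | 0.38 |
| 20 | 0.54 | 0.44 | 0.27 |
| 30 | 0.44 | 0.36 | 0.22 |

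The residual variance of ANCOVA relative to raw change scores is (1 − r²)/[2(1 − r)] = (1 + r)/2. This gives 0.75, 0.85 and 0.95 at r = 0.5, 0.7 and 0.9, a reduction of 25%, 15% and 5%. The precision gain over the tabulated change scores is therefore modest at high r. The main loss is that no difference and no CI are reported at all.

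**Can Tanner transition time be observed?** Protocol 9.1.12.12 stages patients at Visit 2 and at Visit 8 or withdrawal. For a completer, a change is known only to lie within a gap of about 98 days, so it can be counted but not timed. For scale, Protocol Appendix 2 gives stages 2 to 4 age spans of 1.5 to 2 years in both sexes. If those spans are read as time spent in a stage, with patients spread evenly within it, 98/365.25 = 0.268 years. The share moving is then 0.268/2 = 13% to 0.268/1.5 = 18% of patients in those stages. How many patients are in those stages is not stated.

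**Does the protocol's covariate set fit every score?** Not entirely. In SAP Table 7, WPPSI-4 (2;6 to 5;11 years) and NEPSY-2 Word Generation (2 to 5 years) fall inside the 2–5 year stratum, so age group is constant and cannot be fitted. WASI-2 (from 6 years) and Trail Making (from 9 years) cover two of the three strata.

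**The case against.** A reader might infer that the cognition and development parts of the secondary objective get no comparison with placebo. The documents do not support that. SAP 5.5.3.2.9 keeps ANCOVAs for the QOLCE attention/concentration, memory, language, other cognitive and behavior subscales. SAP 5.5.3.2.10 keeps them for Vineland-II. IGF-1 change is still summarized by group, as are height and weight alongside the vital signs. Tanner output was descriptive in the protocol too, so no test was lost there, and patient-level stages remain available in Listing 14.6.

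The sponsor can also say that a descriptive battery is defensible. It has no overall score, the protocol never named which sub-scores to model, and both documents expect partial completion at selected sites. Modelling every score for two doses would produce many tests without multiplicity control (SAP 3.3.2).

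Much of this stands, and it limits both the consequence and the remedy. It does not remove the point. The expectation of partial completion was already in Protocol 9.1.12.6, in the same protocol that promised the ANCOVA, and the SAP does not give it as a reason for dropping the model. QOLCE and Vineland-II are separate protocol endpoints. SAP 5.5.3.2.9 describes QOLCE as parent-reported for ages 4–18, whereas the trial enrolls from age 2 and the battery includes testing by a psychometrician. If descriptive reporting is intended, SAP 5.8 should say so.

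**Conclusion.** The point holds in this form: the cognitive battery loses its planned inferential comparison, Tanner staging loses its planned change count and transition time, neither change is declared in SAP 5.8, and SAP 3.3.2.2 still implies a comparison. This rests on the text alone.

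The consequence is bounded. These are non-hierarchical secondary endpoints, the primary and key secondary conclusions are untouched, and other cognition and behavior measures are still tested. The CI half-widths (0.22 to 0.76 SD) depend on assumed n and r. The 13% to 18% for Tanner depends on even spread within stages and on treating typical ages as durations. All of these should be quoted only as ranges. Omitting transition time is right in substance, since two assessments cannot time a change; only its declaration is missing. The plan should be changed before unblinding.

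**What to change.** 1. **SAP 5.5.3.2.11.** Apply the 5.5.3.2.7 ANCOVA to a short list of scores named in advance, for example the BRIEF composite, BASC-2 composites, ADHD combined score and the main patient-measure standard, scaled or T scores. Use baseline as a covariate, and age group only where the test spans more than one age stratum (omit it for WPPSI-4 and NEPSY-2). Report each dose-minus-placebo difference with its 95% CI, labelled as not multiplicity-controlled. Add the corresponding analysis table to Appendix 5.
2. **SAP 5.6.4.5.** Add a baseline by end-of-treatment Tanner shift table by arm. Show patients at stage 5 at baseline separately, because re-examination is not required for them.
3. **SAP 5.8.** Record that transition time is dropped because two assessments cannot time it. Declare any battery score left descriptive, with the reason, and any decision to omit the p-value that the protocol promised.
4. **SAP 3.3.2.2.** Align the wording with whatever is kept. F-A-S and Animals appears in Table 7 but not in the list of measures to be summarized; settle that in the same edit.

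The cost is a few extra tables from data already collected. The drawback is wide CIs where few patients complete an item.
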